#### **Primary Outcome Measures:**

- Complete re-epithelialization of wound as assessed by the evaluator within 12 weeks after the initial application of the study product plus confirmation of no drainage or need for additional dressing 2 weeks after complete re-epithelialization.

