### **7.4. Interim and Final Analyses**

An unblinded interim assessment for sample size re-estimation (SSR) will be performed on the primary endpoint of the study by an independent statistician. The analysis will be conducted when 50% of the mITT population (24 patients) have been enrolled and completed the primary endpoint evaluation. The analysis described below will be performed on the mITT population.

The purposes of the interim analysis are (1) to calculate the power for superiority, conditioned on the interim-observed difference between treatments with respect to 100% re-epithelialization rates and on the superiority margin of 10%, and (2) determine if the sample size needs to be increased in order to maintain the desired conditional power of 80%.

The conditional power will be calculated under the assumption that the interim observed estimate of the treatment difference is the true treatment difference. It will be calculated using the following formula as discussed in Lan and Wittes (1988) where:

$$1 - \Phi\left[\frac{Z_{1-\alpha} - B_\tau / \tau}{\sqrt{1-\tau}}\right]$$

$Z_{1-\alpha}$  is the  $(1-\alpha) \times 100\%$  percentile of the standard normal distribution (i.e., the critical value used to assess superiority at the final analysis at overall one-sided significance level  $\alpha$ ).

$\tau$  is the information fraction (= proportion of patients in the first interim analysis =  $r/M$  where  $r$  is the number of patients per group in the interim analysis and  $M$  is the planned number of patients per group for the final analysis); if the interim sample sizes per group are not equal due to randomness, the harmonic mean of the sample size will be used.

$B_\tau = Z_\tau \sqrt{\tau}$  where  $Z_\tau$  = the Farrington-Manning non-inferiority test statistic calculated on the interim observed data.  $\Phi$  is the cumulative distribution function of the standard normal distribution.

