Following the “promising zone” algorithm in Mehta and Pocock (2011), if the conditional power based on the planned final sample size of 48 patients is  $<42\%$  or  $>80\%$  at the interim stage, the study will continue as is (there will be no stoppage of the study for futility nor will there be a sample size increase). If the conditional power is between 42-80% (the promising zone), the sample size may then be re-estimated using the method described by Wang et al (2002) in order to maintain 80% conditional power without increasing the Type I error (probability of a false positive result) of the study. Specifically, the total revised sample size per group,  $M'$  required to achieve a conditional power of 80% to assess superiority at the final analysis using a superiority margin of 10% is found by solving the following equation for  $M'$ :

$$Z_{0.20} \sqrt{1 - \frac{r}{M'}} + Z_\tau \sqrt{\frac{M'}{r}} - Z_{1-\alpha} = 0$$

where  $Z_{0.20}$  is the 20th percentile of the standard normal distribution (corresponding to the desired 80% conditional power) and where all other variables in this equation are defined above.  $M'$  will not exceed 70 patients for the DFU arm. This formula assumes the interim observed effect size between treatments is the true effect size between treatments.

Results of the interim assessment will be presented by the independent statistician to the Sponsor group. The report to the Sponsor will state if additional sample is required to achieve a conditional power of 80%, and if so, how many additional patients. If additional sample size is required, the Sponsor will make a decision to either enroll the additional patients or not enroll and accept that the primary

endpoint may be under-powered. The independent statistician's report containing the results that led to the independent statistician's recommendation will be kept confidential within the select Sponsor group.

The following decision rules outline the possible outcomes of the interim analysis:

1. If the test for  $CPni < 0.42$  or  $\geq 0.8$ , then there is no increase in the sample size and the trial will be completed on a minimum of 48 enrolled patients, as scheduled.

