If the test for conditional power is  $0.42 \leq CPni < 0.8$ , then the sample size will be increased by just the right amount such that  $CPni$  is increased to 0.8, under a cap of 70 patients. The range  $0.42 \leq CPni < 0.8$  is called the promising zone for non-inferiority. Specifically, if  $CPni$  is in its promising zone, this decision rule increases the sample size by the smallest of 70 patients or the number needed to boost  $CPni$  to 0.8.

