## **10. SPONSOR DISCONTINUATION CRITERIA**

The Sponsor may suspend or terminate the study or part of the study at any time for any reason. If the investigator suspends or terminates the study at their respective site, the investigator will promptly inform the Sponsor and the IRB/EC and provide them with a detailed written explanation.

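### Section 7.4 does not keep the comparative interim results confidential from the Sponsor, who decides on extra enrolment and can stop the study

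*Combined protocol and SAP*

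**What the plan says.** Section 7.4 starts with a separation of roles: "An unblinded interim assessment for sample size re-estimation (SSR) will be performed on the primary endpoint of the study by an independent statistician". It takes place when 24 of the 48 patients have completed the primary endpoint evaluation.

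The same section then undoes much of that separation. "Results of the interim assessment will be presented by the independent statistician to the Sponsor group". On the underlying material it says: "The independent statistician's report containing the results that led to the independent statistician's recommendation will be kept confidential within the select Sponsor group". It also describes a narrower message, in which the report "will state if additional sample is required to achieve a conditional power of 80%, and if so, how many additional patients".

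The decision lies with the recipient: "If additional sample size is required, the Sponsor will make a decision to either enroll the additional patients or not enroll". The decision rules at the end of Section 7.4 read differently. There, in the promising zone, "the sample size will be increased by just the right amount".

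Section 7.4 provides no futility stop, but Section 10 says: "The Sponsor may suspend or terminate the study or part of the study at any time for any reason". Sections 5.13.5 and 10.1 soften this with a stated intention to use the right only on valid scientific or administrative grounds.

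Sections 3 and 5.7 mask the subject only. The primary outcome in Section 3 is "Complete re-epithelialization of wound as assessed by the evaluator within 12 weeks", with no statement on whether the evaluator is masked. The documents describe no data monitoring committee, no firewall and no membership for the Sponsor group that holds the report.

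**The concern.** An independent statistician is used so that those who run a trial do not learn the comparative results while patients are still being enrolled and assessed. Here the results pass to the party that decides on extra enrolment, can end a site's participation (Section 10.2) and can end the study.

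When this happens, up to half of the planned patients (24 of 48) still have to be assessed, at 2 sites, on an endpoint that involves judgement and with no masking stated for the evaluator. A Sponsor that knows the trend could, without any intent, change how it manages sites, queries wound assessments or handles exits. It could also decline an increase, or stop, after a weak result. Neither action is part of the prespecified rule, and the analysis could not remove the effect of either.

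**Working it through.** The main point is textual, so the first step is to compare what the rule needs with what the plan releases.

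| Item | Needed to run the rule? | Released to the Sponsor under Section 7.4? |
|---|---|---|
| Whether to increase, and by how many | Yes | Yes |
| Results behind the recommendation | No | Yes |
| Discretion to decline the increase | No; the decision rules word it as automatic | Yes |

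The second step is to ask how much the enrolment number alone would reveal.

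**Inputs.** Section 7.4: 24 patients at the interim and 48 planned, so r = 12 and M = 24 per group and τ = 0.5; promising zone of conditional power (CP) 42% to 80%; margin 0.10. Section 7.3: one-sided α = 0.05, closure rates 80% and 40%. Assumptions of this check: exactly 12 v 12 patients, and the cap of 70 read as per group.

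**Formulas (Section 7.4).**
- CP = 1 − Φ[(1.645 − Z/√τ)/√(1 − τ)], where Z is the Farrington-Manning statistic at the interim.
- The revised size per group M' solves −0.8416·√(1 − 12/M') + Z·√(M'/12) − 1.645 = 0.

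**Check against the plan.** CP = 80% gives Z = 1.584 and M' = 24.0, which is the planned size, so the two formulas agree with each other. CP = 42% gives Z = 1.062 and M' = 61.2. Across the zone, each value of M' corresponds to one value of Z.

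**Example.** For 8/12 v 4/12, Z = 1.149. Then CP = 1 − Φ[(1.645 − 1.149/0.7071)/0.7071] = 0.489, and M' = 51.6.

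**All 12 v 12 outcomes in the zone** (matrix v control closures; extra patients = 2 × (M' rounded up − 24)):

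| M' per group | Extra patients | Outcomes | Observed difference |
|---|---|---|---|
| 24.8 | 2 | 8v3, 9v4 | 5/12 |
| 35.0 | 22 | 3v0, 12v9, 5v1, 11v7 | 3/12 or 4/12 |
| 44.4 | 42 | 6v2, 10v6 | 4/12 |
| 49.8 | 52 | 7v3, 9v5 | 4/12 |
| 51.6 | 56 | 8v4 | 4/12 |

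That is 2 + 4 + 2 + 2 + 1 = 11 outcomes. Under 80% v 40% the probabilities are 0.270 below the zone, 0.231 in it and 0.499 above it.

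**Where the illustration weakens.**
- No increase (0.270 + 0.499 = 0.769): the message does not tell a CP below 42% from one of 80% or more.
- Unequal groups: at 13 v 11 (harmonic mean 11.9), M' from 24.3 to 27.4 covers observed differences from 27 to 42 points.
- Cap of 70 in total (35 per group): the last four rows merge. Nine of the 11 outcomes then give the same target, with a difference of 3/12 or 4/12.

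**The case against.** The plan is not careless. An independent statistician does the analysis, the report is to be kept confidential within a chosen group, and one sentence limits the report to whether more patients are needed and how many. Sections 5.13.5 and 10.1 state that the right to stop is meant for valid reasons, and that right is a general clause not tied to the interim.

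Several stronger readings are tempting, and the documents do not support them.
- A reader might infer that a blind is broken. The only declared masking is of the subject, and Section 7.4 does not touch it.
- A reader might infer that Type I error is inflated. The plan makes no early efficacy claim, and Sponsor access does not by itself change the error rate of the planned rule. The risk is to conduct and to discretionary decisions.
- A reader might infer that the Sponsor receives the closure rates outright. The text says only that the report holds the results behind the recommendation, which could be a test statistic or conditional power.
- A reader might infer an unmasked evaluator at the site. The plan is silent on the evaluator's masking and location.
- A reader might infer that the revised size identifies the interim difference exactly. It does not do so in general. Section 7.4 itself allows for unequal groups, and Appendix B uses two strata with blocks of 12 (24 subjects in 2 blocks), so imbalance at 24 patients is plausible.

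What remains is the gap itself. An undefined group is not a safeguard, a stated intention is not a restriction, and the narrow message does not cancel the sentences that place the results with the Sponsor.

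**Conclusion.** The point holds as a low-cost improvement. Section 7.4 does not protect the comparative interim results from the Sponsor, although the rule can run without releasing them. With only the subject masked and no masking stated for the evaluator, this leaves a risk of bias in conduct and in discretionary decisions. The size of that bias cannot be calculated from the documents.

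Confidence is high for the textual gap. The figures on what the target reveals are an illustration that rests on 12 v 12 and a cap of 70 per group. They show that a narrower message reduces the leak without closing it, so the choice of recipients matters as well as the content.

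**What to change.** 1. In Section 7.4, delete the sentence that keeps the results report within the Sponsor group, and replace the sentence on presenting results. Suggested text: The independent statistician will send only the final enrolment target to named Sponsor recipients. Closure rates, the test statistic and conditional power stay with the independent statistician until database lock.
2. State that these recipients take no part in site monitoring, wound-assessment queries or exit decisions.
3. Preferably report the target in coarse steps fixed in advance, so that it maps less closely to the interim statistic.
4. Reconcile the Sponsor's discretion with the automatic wording of the decision rules, so that any increase follows the prespecified rule. State whether the cap of 70 is per group or in total.

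The cost is mainly protocol wording. The Sponsor does not see comparative interim results before lock and gives up its choice to decline an increase. Two limits remain. The target still carries partial information. Also, the allocation lists are printed in Appendix B and the case report forms belong to the Sponsor (Section 8.1), so the new wording protects confidentiality only if access to those is controlled too.

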## 7.5. Statistical Analysis

Data collected in this study will be reported using summary tables and patient data listings. Continuous variables will be summarized using descriptive statistics (number of patients, mean, standard deviation [SD], median, minimum, and maximum). Categorical variables will be summarized using frequencies and percentages of patients in each category. All results will be presented by treatment group and study arm in appropriate patient populations. SAS software version 9.4 or similar will be used for the statistical analysis.

### 7.5.1. Demographic and Baseline Characteristics

Patient demographics for all analysis populations will be summarized in a table. Gender, ethnicity, and race will be summarized with frequency and percent. Age, height, weight, and BMI will be summarized with N, mean, standard deviation, median and minimum and maximum.

### 7.5.2. Medical History

Patient medical history, including tobacco use, comorbidities, diabetes history, and wound history (where applicable) for all analysis populations will be summarized in a table. Categorical variables will be summarized with frequency and percent. Continuous variables will be summarized with N, mean, standard deviation, median and minimum and maximum.

### **7.5.3. Procedural Information**

Descriptive statistics will be used to summarize the initial wound assessment by treatment group and procedural information.

### **7.5.4. Primary Endpoints**

For the purpose of the primary endpoint analysis, the largest study wound will be analyzed.

## **7.6. Study Outcome**

### **7.6.1. Primary Endpoints**

100% re-epithelialization will be assessed every week for 12 weeks or until 100% re-epithelialization, whichever occurs first. Persistence of wound closure will be verified via confirmatory visit within 2 weeks after complete closure has been first determined.

For the primary endpoint of 100% re-epithelialization at week 12 a two-stage analysis will test first if the rate of 100% re-epithelialization is superior between groups using a chi squared and/or Farrington & Manning test. Superiority for synthetic hybrid-scale fiber matrix will be demonstrated if the lower bound of the 90% CI of the difference in proportions lies above the superiority margin of +10%.

### **7.6.2. Secondary Endpoints**

The following secondary endpoints will be summarized for exploratory purposes. Statistical testing may be performed at the request of the sponsor / investigator.

#### Decrease in Wound Area from Baseline

The difference in wound area from baseline to each time point will be summarized for each treatment group in each arm. The difference in mean percent change in size between the treatment group and control group will be calculated for each timepoint. Wound area measurements will be made via acetate tracing every week for 12 weeks, or until 100% re-epithelialization, whichever occurs first.

#### Time to Wound Closure

The time to wound closure will be summarized by proportion of patients with wound closure at each timepoint for each treatment group in each arm. The difference in proportion of patients with wound closure between the treatment group and control group will be calculated for each timepoint.

Persistence of wound closure will be verified via confirmatory visit within 2 weeks after complete closure has been first determined.

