#### **Secondary Outcome Measures:**

- Decrease in Wound Area From Initial Application  
Wound area measurements will be made via acetate tracing every week for 12 weeks or until complete reepithelialization, whichever occurs first.
- Time to Complete Re-epithelialization  
The number of weeks from initial application of study product until complete reepithelialization is first identified.
- Number of Product Applications  
The number of study product applications including the initial application until 12 weeks for DFU patients or until complete reepithelialization, whichever occurs first.

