### **5.6. Randomization**

The randomization process will be finalized prior to enrollment of the first study patient. Once the patient meets all enrollment criteria and has completed the 2-week run-in period, the patient will be randomized. Patients will be randomized to receive either synthetic hybrid-scale fiber matrix (treatment group) or standard of care treatment (control group). Appendix B presents the randomization plan.

Randomization will be stratified by wound size:

Patients will fall into two groups ( $< 12.5 \text{ cm}^2$ ) and ( $\geq 12.5 \text{ cm}^2$  and  $\leq 30 \text{ cm}^2$ ). Patients within each group will be randomized in a 1:1 ratio to receive either synthetic hybrid-scale fiber matrix or standard of care treatment.

Once the patient is ready to be randomized, the randomization form will be completed by study personnel. Any patients that exit the study before randomization

are considered screen failures. A study exit CRF shall be completed if the patient is not eligible for randomization.

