## **5.12. Follow-Up Procedures**

Weekly up to 12 weeks or until complete closure is first identified with a confirmation visit within 2 weeks thereafter; window for all visits is  $\pm$  3 days. At each of the interim timepoints subjects will return to the clinic for analysis / assessment of the following as indicated in the Schedule of Events in Appendix A:

- Measurement of wound area
- Documentation of wound appearance via photograph
- Documentation of wound closure (if present)
- Gross observation of wound for evidence of infection
- Assessment of Quality of Life
- Codes used to submit for reimbursement and amount (if any) reimbursed

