### **7.3. Sample Size Calculation**

Sample size calculations were performed using a Farrington & Manning test for superiority of the synthetic hybrid-scale fiber matrix group compared to the control group. Under assumptions of a closure rate of 80% for the synthetic hybrid-scale fiber matrix group, 40% for the control group, and a superiority margin of 10%, this results in a sample size of 20 per group (40 total) that provides a power of 0.8 and one-sided alpha of 0.05. After allowing for an assumed 20% lost to follow up, this results in a total sample size of 48 patients.

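### Time to wound closure is summarised only as weekly proportions, with no stated denominator, censoring rule or single between-arm comparison

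*Combined protocol and SAP*

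**What the plan says.** Section 3 (Secondary Outcome Measures) defines the endpoint as a duration: "The number of weeks from initial application of study product until complete reepithelialization is first identified".

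Section 7.6.2 (Time to Wound Closure) gives the analysis: "The time to wound closure will be summarized by proportion of patients with wound closure at each timepoint", and then "The difference in proportion of patients with wound closure between the treatment group and control group will be calculated for each timepoint". It does not say who is in the denominator, and it names no censoring rule, survival curve, median, hazard ratio or test. The opening of Section 7.6.2 sets the status of the endpoint: "The following secondary endpoints will be summarized for exploratory purposes". It adds: "Statistical testing may be performed at the request of the sponsor / investigator". No method is given for such a test.

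Four other places bear on the point:
- Section 5.12 sets visits as "Weekly up to 12 weeks or until complete closure is first identified", so healed patients leave the weekly schedule.
- Section 5.13.1 lists amputation, death, withdrawal and loss to follow-up as exits.
- Section 7.3 sizes the trial "After allowing for an assumed 20% lost to follow up".
- Section 5.6 states: "Randomization will be stratified by wound size", in two strata split at 12.5 cm².

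**The concern.** A duration with incomplete follow-up is analysed as a series of binary snapshots. Three things are left open.

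- **Denominator.** A patient lost at week 3 can be kept as not closed, removed, or given an imputed status. Section 7.6.2 does not choose, and the choices give different numbers.
- **Dropout.** If loss differs between arms, an all-patient difference mixes healing speed with retention. Only the subject is masked (Section 3), so unequal retention cannot be ruled out.
- **Comparison.** Up to 12 correlated weekly differences come with optional testing by an unnamed method. Both the week and the test could be chosen after the data are seen.

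This matters because Section 2.2 puts time to epithelialization among the outcomes that the study will demonstrate, and says the data are valuable for payors' coverage decisions. The pilot reported an average time to closure of 6.4 weeks (Section 2.1). Section 7.6.2 plans no time estimate to set beside it.

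**Working it through.** The plan states no figure for time to closure, so there is none to reproduce. The check asks what the planned summary would show under the plan's own assumptions.

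**Inputs from the plan.** Closure of 80% and 40%, 20% loss, one-sided alpha 0.05 and 24 per arm (Sections 1 and 7.3); weekly visits to week 12 (Section 5.12).

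**Assumptions added here.** Closure times are exponential. Dropout has a constant hazard and is unrelated to healing. The 20% is the chance of dropping out by week 12 if the wound does not close first.

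**1. Hazards per week.** λ = −ln(1 − p)/12 and δ = −ln(1 − q)/12, where p is closure and q is dropout by week 12.
- Restrata: −ln(0.2)/12 = 0.1341
- Control: −ln(0.6)/12 = 0.0426
- Dropout: −ln(0.8)/12 = 0.0186

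**2. Proportion seen to close, over all patients.** Sum over weeks 1 to 12 of (e^(−λ(w−1)) − e^(−λw)) × e^(−δw). This equals (e^λ − 1) × r(1 − r^12)/(1 − r), with r = e^(−(λ+δ)).
- Restrata: r = 0.8584 and r^12 = 0.2 × 0.8 = 0.16, so 0.1435 × 0.8584 × 0.84/0.1416 = 0.731
- Control: r = 0.9407 and r^12 = 0.6 × 0.8 = 0.48, so 0.04349 × 0.9407 × 0.52/0.05933 = 0.359

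**3. Known status only.** Closed/(closed + still open and present at week 12).
- Restrata: 0.731/(0.731 + 0.16) = 0.82
- Control: 0.359/(0.359 + 0.48) = 0.43

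**4. Kaplan-Meier.** Among patients still followed, the chance of closing at each visit is 1 − e^(−λ), which independent dropout does not change. The estimate at week 12 is therefore 1 − e^(−12λ), or 0.80 and 0.40.

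| Week-12 closure, 20% dropout in both arms | Restrata | Control | Difference |
|---|---|---|---|
| Assumed truth | 80% | 40% | 40 |
| All patients, losses not closed | 73% | 36% | 37 |
| Known status only | 82% | 43% | 39 |
| Kaplan-Meier | 80% | 40% | 40 |

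Under this model only 1 − 0.731 − 0.16 = 11% of Restrata and 1 − 0.359 − 0.48 = 16% of control patients are actually lost unhealed. If the plan's 20% means patients lost before closure, the all-patient shortfall is larger.

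**5. Unequal dropout, all-patient proportions.** The formula in step 2 gives:
- 30% Restrata, 10% control: 0.693 − 0.380 = 0.31. Counting closure in continuous time, λ/(λ+δ) × (1 − e^(−12(λ+δ))), gives 0.704 − 0.381 = 0.32.
- 10% Restrata, 30% control: 0.766 − 0.336 = 0.43. Continuous time also gives 0.43.

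**6. Power, no margin, one-sided 0.05.** The closure hazard ratio is ln(0.2)/ln(0.6) = 3.15. Without dropout, 48 patients give 48 × 0.60 = 28.8 closures. Schoenfeld's formula, Φ(ln(3.15) × √28.8/2 − 1.645), gives 92%. Simulation at 24 per arm with weekly visits compares the log-rank test with a week-12 proportion test that counts losses as not closed:

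| Dropout | Log-rank | Week-12 proportion |
|---|---|---|
| 0% | 92% | 91% |
| 20% | 89% | 86% |
| 30% | 88% | 83% |

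The stratified log-rank test at 20% dropout has 89% to 96% power, against 86% to 89% for the proportion. This is over assumed small-wound shares of 50% to 75% and large-wound closure hazards of 1.0 to 0.3 times the small-wound hazard.

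**The case against.** **The endpoint is exploratory.** It carries no alpha, success criterion or planned test. This stands. A reader might infer that the trial's main conclusion is at risk. It is not, because the primary endpoint has its own analysis.

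**Kaplan-Meier wins because dropout was assumed independent of healing.** This stands too. Take the opposite extreme, where 20% drop out and all of them would not have healed by week 12. The all-patient proportions are then right at 80% and 40%, while Kaplan-Meier rises to about 96% or more against about 45%. The documents do not say which mechanism to expect, so it cannot be claimed that Kaplan-Meier always recovers the truth.

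**The weekly proportions do carry information on time.** A reader might infer that the plan can never yield a time. That is too strong. With complete follow-up the cumulative proportions equal 1 minus Kaplan-Meier, and a median can be read from them. Section 7.5 also has a general rule giving means and medians for continuous variables, but Section 7.6.2 does not apply it to time. Applied to healed patients only, it would mislead: in the simulation with 20% dropout and no effect of wound size, mean time among healers is about 4.8 and 5.8 weeks, while the assumed medians are 5.2 and 16.3 weeks.

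**Losses need not be counted as failures or dropped.** Section 7.8 plans multiple imputation of closure status and leaves details to a formal analysis plan. But it ties the combined result to the primary endpoint test and says nothing of weekly status or time.

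**A denominator of patients attending each visit would be absurd.** A reader might infer one, since healed patients stop attending. Section 7.6.2 does not say so, and cumulative closure is the ordinary reading. The supportable criticism is that the denominator is not stated.

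**The gain is small.** With equal dropout the difference moves from 40 to about 37 points. A 20-point imbalance in dropout is nowhere predicted. The power gain is modest on an endpoint with no required test.

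**Conclusion.** The concern holds in a limited form. The endpoint is a time, but the named analysis is a set of weekly proportions and differences without a denominator, censoring rule or single comparison, in a trial that expects 20% loss.

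Under exponential closure and dropout unrelated to healing, the choice of denominator moves week-12 closure by about 9 points in the Restrata arm (73% or 82%) and 7 in the control arm (36% or 43%). Arm-specific dropout of 30% and 10% moves the all-patient difference to about 31 to 32 or 43 points, against 40. These sizes depend on the assumed dropout pattern.

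The case rests on prespecification and on the handling of losses. Power is a minor part of it: about 3 points for the unstratified test at 20% dropout. The change is worth making, but the primary result does not depend on it.

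**What to change.** Amend Section 7.6.2 (Time to Wound Closure) as follows:

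- Name Kaplan-Meier curves as the analysis, reporting the proportion closed by week with confidence intervals, and the median time by arm where it is reached.
- Name one comparison: a log-rank test stratified by the two wound-size strata of Section 5.6. State that it remains exploratory.
- Censor unhealed patients at their last wound assessment or at week 12. Count amputation and death as not closed through week 12, because censoring them would treat closure as still possible.
- Keep the weekly proportions as a supporting table, over all patients with losses counted as not closed. This also serves as a sensitivity analysis for dropout related to non-healing.

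The cost is a few sentences and one standard procedure in the software named in Section 7.5. No new data are needed, because closure is already assessed weekly.

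The limits should be written down as well. Kaplan-Meier assumes dropout unrelated to healing. Weekly visits create tied times, so the method for ties should be stated. At the assumed 40% closure the control median would probably not be reached by week 12 and should be reported as such.
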